### 7.6.2 Subject Information

Summaries and listings will be provided for all subjects who received at least 1 dose of study drug and provided at least 1 safety or efficacy evaluation. Subject disposition summaries will include the number of enrolled subjects, the number of subjects receiving study medication, the number of subjects completing the study, and the reasons for discontinuation. Demographic variables include age, sex, and race.

### 7.6.3 Populations Analyzed

**Full Analysis Set:** The full efficacy set will include all subjects with a baseline measurement and at least one post-baseline measurement. This set will be used for the primary analyses of all efficacy endpoints.

**Safety Analysis Set:** The safety analysis set consists of all subjects who receive at least one dose of study drug. This set will be used for the analyses of all safety endpoints.

**Sialic Acid Analysis Set:** The SA analysis set will consist of all randomized subjects with evaluable free serum SA levels.

### 7.6.4 Efficacy Analysis

Separate analyses will be performed for subjects coming from each parent study.

The full analysis set will include all subjects with a baseline measurement and at least one post-baseline measurement. This set will be used for the analyses of all efficacy endpoints.

Baseline values for each endpoint will be defined as the last scheduled data collection visit before first dose according to the Schedule of Events ([Table 2.1](#)).

Efficacy analyses will use generalized estimating equation (GEE) to evaluate trends over time with respect the changes from baseline for the primary efficacy endpoint, and all secondary and tertiary efficacy endpoints. Baseline will be included as a covariate in the model. This method will be the primary analysis method for all repeated measures endpoints.

The statistical analyses will be reported using summary tables, figures, and data listings.

Statistical tests will be 2-sided at the alpha=0.05 significance level.

Continuous variables will be summarized with means, standard deviations, medians, minimums, and maximums. Categorical variables will be summarized by counts and by percentages of subjects in corresponding categories.

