#### **7.4.4 Method of Assigning Subjects to Treatment Groups**

This is an open-label study and consists of one treatment arm. All subjects will receive Ace-ER 6g/day.

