### 7.5.2 Efficacy Measures

Efficacy will be evaluated by changes in upper and lower extremity muscle strength and function, and physical functioning. Results from baseline assessments will be compared with those of post-treatment assessments listed in the Schedule of Events ([Table 2.1](#)), with efficacy conclusions based on change from baseline over the treatment period.

The following section describes the assessments that will be performed throughout the study to derive efficacy variables. However, only applicable assessments based on the subject's parent study prior to roll-over should be administered to each subject. For UX001-CL202 subjects, assessments that cannot be safely performed by a subject due to disease progression should not be administered.

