8 STATISTICAL METHODS OF ANALYSES

8.1 General Principles

All statistical tests will be two-sided and a difference resulting in a p-value of less than or equal to 0.05 will be considered statistically significant. All p-values will be rounded to and displayed in four decimals. If a p-value less than 0.0001 occurs, it will be shown in the table as <0.0001.

Continuous variables will be summarized by number of subjects and mean, SD/SE, median, minimum, and maximum values. Categorical variables will be summarized by number and percentage. No imputation on missing data will be made, unless stated otherwise.

Data collected will be presented in listings. Data not subject to analysis according to this plan will not appear in any tables or graphs but will be included in the data listings.

Post-hoc exploratory analyses not identified in this SAP may be performed to further examine the study data. These analyses will be clearly identified as such in the final clinical study report. The SAP will not be amended for post-hoc or additional analyses identified after planned analyses are completed. Similarly, additional tables and figures may be defined to further evaluate study results and the SAP will not be amended to list them.

Efficacy analyses will be presented by the parent study as illustrated in [Table 8.1.1](#): UX001-CL301, CL202 or CL203. Different efficacy endpoints at different scheduled time points were collected depending on which parent study the subjects were enrolled from.

Safety analyses will be presented by the parent studies and overall as illustrated in [Table 8.1.1](#). Subjects enrolling from UX001-CL301 will be further examined by the treatment group assigned in the parent study: placebo, Ace-ER 6 g/day, and All.

[Table 8.1.1](#) also provides the guidance for the treatment groups to be displayed for biomarker analyses as well as efficacy analyses and safety analyses, which have been described above. Baseline used for the analyses are specified as well. Example table templates are provided in [Appendix 10.6](#) for efficacy and safety.

Table 8.1.1: Analysis Presentation

Analysis Category	Analysis Set	Parent Study	Treatment Group	Baseline Applied	
Week 96/ET efficacy analysis	Full Analysis Set	CL301	Placebo*	Parent Study Baseline	
			Ace-ER 6 g/day		
			Placebo*	Current Study Baseline	
			ACE-ER 6 g/day		
			All		
Week 96/ET efficacy analysis	Full Analysis Set	CL202	Ace-ER 6 g/day	Current Study Baseline	

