8.6 Efficacy Analysis

Efficacy analyses will use generalized estimating equation (GEE) (Hanley et al. 2003) to evaluate trends over time with respect to the changes from baseline for all continuous efficacy endpoints. Baseline will be included as a covariate in the model. GEE will be the primary analysis method for all repeated measures endpoints. The statistical analyses will be reported in summary tables, figures, and data listings. Statistical tests will be 2-sided at the alpha=0.05 significance level.

Efficacy analysis will be based on the full analysis set.

Additional efficacy analyses may be performed for subjects enrolled in CL301 by incorporating data from both the parent study and the current study to compare the placebo versus UX001 treatment groups using the methodology described in ([Hu et al. 2007](#)). Such analyses examine the extended treatment effect of UX001 on the placebo subjects who now are taking UX001 in the extension study.

Parent study baseline will be used to evaluate the long-term study drug effect from the parent study drug administration, except for subjects enrolling from CL202.

Current study baseline will be used to evaluate the continuous long-term study drug effect going on after the parent study.

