10 APPENDICES

10.1 Summary of Efficacy Endpoints and Analyses

Test / Instrument	Endpoint	Type of analysis	Time points for Assessment	Statistical approach at week 96/ET analysis
Subjects enrolling from UX001-202 and UX001-301				
Physical therapy – Hand-held Dynamometry (HHD)	The changes from baseline in Upper Extremity Composite (UEC) Score based on bilateral strength recorded in the following muscle groups: gross grip, shoulder abductors, elbow flexors, and elbow extensors	Primary analysis	Weeks 8, 16, 24, 48, 72, and 96	GEE Model
GNEM Functional Activities Scale (GNEM-FAS)	Changes from baseline on Upper Extremity Domain score	Secondary efficacy analysis	Weeks 8, 16, 24, 48, 72, and 96	GEE Model
	Changes on Mobility Domain score			
Physical therapy – Hand-held Dynamometry (HHD)	Changes from baseline in lower extremity composite score (LEC) based on bilateral strength recorded in the following muscle groups: knee flexors, hip flexors, hip extensors, hip abductors and hip adductors.	Secondary efficacy analysis	Weeks 8, 16, 24, 48, 72, and 96	GEE Model
	Changes from baseline in total force and percent predicted total force in the Knee Extensors.			
Sit to Stand	Change from baseline in the number of stands in the Sit-to-Stand test	Secondary efficacy analysis	Weeks 8, 16, 24, 48, 72, and 96	GEE Model
Weighed Arm Lift Test	Changes from baseline in the number of lifts in 30 second weighted arm lift tests	Secondary efficacy analysis	Weeks 8, 16, 24, 48, 72, and 96	GEE Model
6-Minute Walk Test	Changes from baseline in meters walked in 6MWT and percent predicted	Secondary efficacy analysis	Weeks 8, 16, 24, 48, 72, and 96	GEE Model

Test / Instrument	Endpoint	Type of analysis	Time points for Assessment	Statistical approach at week 96/ET analysis
Physical therapy – Hand-held Dynamometry (HHD)	Changes from baseline in UEC and LEC percent predicted based on reference equations adjusting for age, gender, height, and weight.	Tertiary efficacy analysis	Weeks 8, 16, 24, 48, 72, and 96	Summary statistics
	Changes from baseline in bilateral total force and percent predicted total force for each individual muscle group included in the UEC and LEC.			Summary statistics
GNEM Functional Activities Scale (GNEM-FAS)	Changes from baseline on the total score on the GNEM-FAS	Tertiary efficacy analysis	Weeks 8, 16, 24, 48, 72, and 96	Summary statistics
	Changes from baseline on the Self-Care Domain Score on the GNEM-FAS			Summary statistics

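### In a single-group model, baseline as a covariate makes the standard error of a within-cohort mean change too small, by an amount set by a correlation that the plan does not give

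*Protocol*

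**What the plan says.** Protocol 7.6.4 models changes from baseline by GEE and states "Baseline will be included as a covariate in the model". SAP 8.6 repeats that sentence, and the SAP takes precedence on analysis methods (SAP 1).

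On design, Protocol 7.4.4 says "This is an open-label study and consists of one treatment arm", and Protocol 7.6.4 says "Separate analyses will be performed for subjects coming from each parent study". SAP Table 8.1.1 shows CL202 and CL203 as single groups. It shows CL301 by former treatment and, for the current-study baseline, also as All.

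On what is tested, SAP 8.6 uses GEE to "evaluate trends over time with respect to the changes from baseline for all continuous efficacy endpoints", while Protocol 7.5.2 describes the evaluation "with efficacy conclusions based on change from baseline over the treatment period". SAP 10.1 has a column headed "Statistical approach at week 96/ET analysis". Neither document names the tested contrast, the baseline value at which an adjusted mean is taken, the working correlation or the type of standard error.

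On the level, Protocol 7.6.4 says "Statistical tests will be 2-sided at the alpha=0.05 significance level", and SAP 8.1 adds that "a difference resulting in a p-value of less than or equal to 0.05 will be considered statistically significant".

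**The concern.** Adjusting for baseline sharpens a comparison between groups. In a single-group analysis there is no such comparison, and an obvious question is whether the mean change differs from zero. The baseline mean is itself part of the change score, so its sampling error belongs in the standard error. A regression on baseline, read off at the observed mean baseline, treats that mean as known. The robust GEE variance does the same.

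Measurement error makes change correlate negatively with baseline. A cohort that happens to be measured low at entry will then tend to show a gain, and one measured high a decline, and either is called significant too often. At stake is the error rate of any p-value or interval for within-cohort mean change in strength or function.

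**Working it through.** **Inputs from the documents.** Two-sided level 0.05. Planned cohorts 55 (CL202), 80 (CL301) and 30 (CL203), and 55 + 80 + 30 = 165, as Protocol 7.6.1 states (the SAP says about 180, without a split). Six post-baseline visits for CL202 and CL301, four for CL203 (SAP 10.1).

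**Assumed, because not in the documents.** Equal SD *s* at all visits, and correlation *r* between baseline and follow-up of 0.95 to 0.7 (exchangeable across visits). Unequal SDs are considered below.

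**The plan's own figure.** 2(1 − Φ(1.960)) = 0.050. No power or other operating characteristic is stated.

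**Week 96 mean change, complete data.**
- True variance of a change: 2s²(1 − r).
- Residual variance given baseline: s²(1 − r²).
- Ratio of reported to true SE: √[(1 − r²) / (2(1 − r))] = √[(1 + r)/2].
- Actual size: 2(1 − Φ(1.96 × ratio)).
- The missing term: the slope of change on baseline is b = −(1 − r), so b²s² = s²(1 − r)². Adding it gives s²(1 − r²) + s²(1 − r)² = 2s²(1 − r), the true variance.

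**Change averaged over V visits.** The true variance is s²(1 − r)(1 + 1/V) and the residual variance is s²(1 − r)(r + 1/V), so the ratio is √[(r + 1/V)/(1 + 1/V)]. For r = 0.7 and V = 6: √(0.867/1.167) = 0.862.

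| r | Week 96 SE ratio | Week 96 size | Six-visit SE ratio | Six-visit size |
|---|---|---|---|---|
| 0.95 | 0.987 | 5.3% | 0.978 | 5.5% |
| 0.9 | 0.975 | 5.6% | 0.956 | 6.1% |
| 0.8 | 0.949 | 6.3% | 0.910 | 7.4% |
| 0.7 | 0.922 | 7.1% | 0.862 | 9.1% |

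**Simulation, null true, 20,000 runs per cell.** Week 96 t test, n = 80, at r = 0.95, 0.9, 0.8 and 0.7:
- With the covariate: 5.2%, 6.0%, 6.4%, 7.2%.
- Without it: 5.0%, 5.4%, 5.0%, 5.1%.

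At r = 0.7 the test with the covariate ran at 6.9% (n = 30) and 6.8% (n = 55), so within the planned cohort sizes the inflation does not depend on n. With a robust SE and a z test at n = 80, r = 0.7, the figures are 8.1% with and 5.6% without. The excess of 5.6% over 5% is small-sample sandwich error, a separate matter.

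**One fitted GEE (n = 80, r = 0.7, exchangeable).**
- Week 96 estimate 0.19683 in both models. SE 0.07869 without the covariate and 0.07352 with it.
- Time slope 0.00013, SE 0.00076 in both. In simulation the size of the slope test was identical with and without baseline.

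**Unequal SDs (follow-up/baseline ratio k).** The correlation of change with baseline is c = (rk − 1)/√(1 + k² − 2rk), and the SE ratio is √(1 − c²). Over r = 0.95 to 0.7 the Week 96 size is 7.8% to 8.9% for k = 0.9, 5.0% to 6.0% for k = 1.1, and 5.0% to 6.6% for k = 1.2. The inflation vanishes where change is uncorrelated with baseline.

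**Missing visits that depend on baseline.** Assume Week 96 is missing for 50% of subjects below the baseline mean and 10% above it.
- First run (n = 80, 20,000 runs, robust SE, independence working correlation; r = 0.9, 0.8, 0.7): change with visit terms only rejected 7.4%, 9.1% and 10.9%, with biased estimates. The planned model, evaluated at the full-set mean baseline, rejected 6.2%, 6.6% and 7.1% and was unbiased.
- Second run, same missingness rates: visit terms only 7.6% to 12.2% with bias, planned model 6.5% to 7.9%, Week 0 as first response 5.7% to 6.5% and essentially unbiased.

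**The case against.** The strongest reply is that the plan does not specify the test being criticised. It speaks of trends over time and names no adjusted mean, no test against zero and no average over visits. If the tested quantity is a slope, complete-visit results do not depend on the covariate. This stands, and it makes the point conditional. It does not remove it: Protocol 7.5.2 rests efficacy conclusions on change from baseline, and mean change by visit is a natural output of the planned model.

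Second, conditioning on baseline protects against missingness that depends on baseline. The plan uses observed data (SAP 8.1), and CL202 assessments made unsafe by progression are omitted (Protocol 7.5.2). This also stands. A reader might infer that the covariate is either idle or harmful and should be removed. The missing-visit calculation shows otherwise.

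Third, the smaller SE is valid if inference is meant to be conditional on the enrolled subjects' baselines. Neither document declares that target, and the stated objective concerns the effect in subjects with GNE myopathy (SAP 2.2). Conditional on the observed baselines, regression to the mean makes the expected change non-zero even when the population mean is constant.

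Fourth, the by-visit templates in SAP 10.7 already show unadjusted mean change with SD, so the unadjusted SE can be recovered. Inflation is also two-sided, so false declines are as likely as false gains. Both are fair and limit the harm.

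**Conclusion.** The point holds for tests of within-cohort mean change at the observed mean baseline: CL202, CL203 and the CL301 All group. Under equal variances and r = 0.95 to 0.7, the Week 96 SE is 1.3% to 7.8% too small and the 5% test runs at about 5.3% to 7.1%. For a six-visit average the SE is 2.2% to 13.8% too small and the size about 5.5% to 9.1%. These ranges rest on assumed correlations and SDs. For very reliable measures the effect is slight.

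A reader might infer that every cohort and every efficacy endpoint is affected. The documents do not support that. A slope with complete visits is unaffected. Contrasts between former placebo and Ace-ER subjects in CL301 (SAP 8.6) properly keep the covariate. SAP 10.1 assigns summary statistics, not GEE, to the CL202/CL301 tertiary endpoints. The six-visit figure does not apply to CL203, which has four post-baseline visits.

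Safety is the primary objective, so this is a modest point, worth a short correction.

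**What to change.** In SAP 8.6, name the tested contrast. For within-cohort mean change, use one of these:

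- **Preferred:** include Week 0 (or the parent-study baseline where Table 8.1.1 applies it) as the first response in the repeated-measures GEE, with a visit factor and a non-independence working correlation such as exchangeable, and test visit minus baseline. The working correlation matters: under independence, subjects with a missing visit contribute to the baseline mean but not to the visit mean, and the bias returns.
- **Alternative:** keep the covariate, evaluate at the full-set mean baseline, and add b²·Var(X)/n to the squared SE, where b is the slope of change on baseline, Var(X) the baseline variance and n the number of subjects in that mean. This assumes a slope common to the visits.

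Do not simply drop baseline and fit visit terms only. Keep it as a covariate for between-group contrasts in CL301.

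The cost is a few sentences. Relative to the planned SE, the corrected one is wider by 1/0.987 − 1 = 1.3% to 1/0.922 − 1 = 8.5% at Week 96, and by 1/0.978 − 1 = 2.2% to 1/0.862 − 1 = 16% for a six-visit average, under the assumed correlations. That is its correct size. Complete-data point estimates do not change.

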#### **7.6.5 Analyses of Drug Concentration Measurements**

The SA analysis set will be used to evaluate free serum SA levels and urine SA levels (free, bound and total; corrected for creatinine) at trough (pre-dose) using the SA analysis set. Changes from baseline will be analyzed using the GEE method for repeated measures analysis.

#### **7.6.6 Safety Analyses**

Safety will be evaluated for the overall study population as well as for subjects from the UX001-CL202, UX001-CL301, and UX001-CL203 study.

The safety analysis set will be used for the analyses of all safety endpoints. Safety will be evaluated by the incidence, frequency and severity of AEs and SAEs, and clinically significant changes from study baseline to scheduled time points in:

- Interval history
- Vital signs
- Physical examination findings
- Clinical laboratory evaluations
- Suicidal ideation and behavior assessments (C-SSRS)
- Concomitant medications

All AEs will be coded using the Medical Dictionary for Regulatory Activities (MedDRA). The incidence and frequency of AEs will be summarized by System Organ Class (SOC), Preferred Term (PT), severity, and relationship to treatment. The numbers (frequency) and incidence rates of AEs and SAEs will be summarized by treatment group. A by-subject listing will be provided for those subjects who experience a SAE, including death, or experience an AE associated with early withdrawal from the study or study drug treatment.

Clinical laboratory data will be summarized by the type of laboratory test. The frequency and percentage of subjects who experience abnormal clinical laboratory results (i.e. outside of reference ranges) and/or clinically significant abnormalities will be presented for each clinical laboratory measurement. For each clinical laboratory measurement, descriptive statistics will be provided for study baseline and all subsequent post-treatment scheduled visits. Changes from study baseline to the post-treatment visits will also be provided.

Changes in findings from study baseline physical examinations will be tabulated for each subject by examination category. If there are examination findings that change in more than one subject, these will be tabulated in a separate table and expressed as the number of subjects with the change out of the total. No statistics will be applied to the physical examination findings.

The SAP will provide additional details on the planned safety analyses.

## 8 STUDY CONDUCT

### 8.1 Ethics

#### 8.1.1 Institutional Review Board or Ethics Committee

The Institutional Review Board (IRB)/Ethics Committee (EC) must be a properly constituted board or committee operating in accordance with 21 Code of Federal Regulations (CFR) Part 56, "Institutional Review Boards." This protocol, any protocol amendments, and the associated informed consent forms (ICFs) must be submitted to the IRB/EC for review and must be approved before screening of any subject into the study. Study drug may not be shipped to the Investigator until Ultragenyx or its designee has received a copy of the letter or certificate of approval from the IRB/EC for the protocol and any protocol amendments, as applicable.

All subject recruitment and/or advertising information must be submitted to the IRB/EC and Ultragenyx or its designee for review and approval prior to implementation. IRB/EC approval of any protocol amendments must be received before any of the changes outlined in the amendments are put into effect, except when the amendment has been enacted to protect subject safety. In such cases, the chair of the IRB/EC should be notified immediately and the amendment forwarded to the IRB/EC for review and approval.

#### 8.1.2 Ethical Conduct of Study

This protocol is written in accordance with the principles established by the 18th World Medical Association General Assembly (Helsinki, 1964) and subsequent amendments and clarifications adopted by the General Assemblies. The Sponsor and Investigator will make every effort to assure the study described in this protocol is conducted in full conformance with those principles, current FDA regulations, ICH Good Clinical Practices (GCP) guidelines, and local ethical and regulatory requirements. Should a conflict arise, the Sponsor and Investigator will follow whichever law or guideline affords the greater protection to the individual subject. The investigator will also make sure he or she is thoroughly familiar with the appropriate administration and potential risks of administration of the study drug, as described in this protocol and the IB, prior to the initiation of the study.

#### 8.1.3 Subject Information and Consent

Appropriate forms for documenting written informed consent will be provided by the Investigator and reviewed and approved by Ultragenyx or its designee before submission to the IRB/EC. Ultragenyx or its designee must receive a copy of the IRB/EC's approval of the informed consent form (ICF) before the shipment of study drug to the study site.

It is the Investigator's responsibility to obtain signed written informed consent from each potential study subject prior to the conduct of any study procedures. This written informed consent will be obtained after the methods, objectives, requirements, and potential risks of the study have been fully explained to each potential subject. The Investigator must explain

to each subject that the subject is completely free to refuse to enter the study or to withdraw from it at any time.

The method of obtaining and documenting informed consent and the contents of the ICF will comply with ICH GCP guidelines, the requirements of 21 CFR Part 50, “Protection of Human Subjects,” the Health Insurance Portability and Accountability Act (HIPAA) regulations, and all other applicable regulatory requirements. Subjects will be given a copy of the signed ICF and will be provided any new information during the course of the study that might affect their continued participation in the study. The Investigator or a qualified designee will be available to answer each subject's questions throughout the study, and all of the subject's questions must be answered to the subject's satisfaction. If the protocol is amended and the ICF is revised, each subject will be required to provide written informed consent again using the revised ICF.

The date of written informed consent will be documented in each potential subject's CRF. The signed ICF will remain in each subject's study file and must be available to the study monitor(s) at all times.

